9.3. Vital Sign Measurements

Vital sign measurements will include temperature (°C; tympanic or oral), respiratory rate, supine systolic and diastolic pressure, and pulse.

Vital sign measurements will be performed at below timepoint:

First participant within each cohort	Subsequent participants within each cohort
Screening	Screening
Day 1 (pre-dose, 2h, 6h, and 12h post IV	Day 1 (pre-dose, 2h, 6h, and 12h post IV
dose)	dose)
Day 2 (24 hours post IV dose)	Day 2 (24 hours post IV dose)
Day 3 (48 hours post IV dose)	Day 3 (48 hours post IV dose)
Day 5 (96 hours post IV dose)	Day 5 (96 hours post IV dose)
Day 8 (1 week post IV dose)	
Day 15 (pre-dose, 2h, 6h, and 12h post SC	Day 8 (pre-dose, 2h, 6h, and 12h post SC dose
dose 1)	1)
Day 16 (24 hours post SC dose 1)	Day 9 (24 hours post SC dose 1)
Day 17 (48 hours post SC dose 1)	Day 10 (48 hours post SC dose 1)
Day 19 (96 hours post SC dose 1)	Day 12 (96 hours post SC dose 1)
Day 22 (pre-dose, 2h, 6h, and 12h post SC	Day 15 (pre-dose, 2h, 6h, and 12h post SC
dose 2)	dose 2)
Day 23 (24 hours post SC dose 2)	Day 16 (24 hours post SC dose 2)
Day 29 (pre-dose, 2h, 6h, and 12h post SC	Day 22 (pre-dose, 2h, 6h, and 12h post SC
dose 3)	dose 3)
Day 30 (24 hours post SC dose 3)	Day 23 (24 hours post SC dose 3)
Day 31 (48 hours post SC dose 3),	Day 24 (48 hours post SC dose 3)
Day 36 (168 hours post SC dose 3)	
Day 36 (1 week post SC dose 3)	Day 29 (168 hours/1 week post SC dose 3)
Day 51 (3 weeks post SC dose 3)	Day 43 (3 weeks post SC dose 3)
Day 65 (5 weeks post SC dose 3)	Day 57 (5 weeks post SC dose 3)
Day 85/ED/EoS (8 weeks post SC dose 3)	Day 78/ED/EoS (8 weeks post SC dose 3)

Relative time to dose will be presented for summary statistics which includes:

- Baseline, 2 hours post IV dose, 6 hours post IV dose, 12 hours post IV dose, 24 hours post IV dose, 48 hours post IV dose, 96 hours post IV dose, and 1 week post IV dose;
- Pre SC dose 1, 2 hours post SC dose 1, 6 hours post SC dose 1, 12 hours post SC dose 1, 24 hours post SC dose 1, 48 hours post SC dose 1, and 96 hours post SC dose 1;

- Pre SC dose 2, 2 hours post SC dose 2, 6 hours post SC dose 2, 12 hours post SC dose 2, 24 hours post SC dose 2;
- Pre SC dose 3, 2 hours post SC dose 3, 6 hours post SC dose 3, 12 hours post SC dose 3, 24 hours post SC dose 3, 48 hours post SC dose 3, 1 week post SC dose 3, 3 weeks post SC dose 3, 5 weeks post SC dose 3, and 8 weeks post SC dose 3.

Summary statistics and change from baseline for vital signs (temperature, respiratory rate, pulse, and systolic and diastolic blood pressure) will be presented by relative time to dose.

Vital sign measurement results, including height, weight, and BMI, will be presented in a data listing.

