Hypersensitivity reaction labs (tryptase, IgE, C5b-9, chemistry, hematology, and urinalysis)	Х					$\leftarrow X^i\!\!\rightarrow$					
Concomitant medications			←Monitor	continual	ly after ICF is	signed→					
Adverse events review/evaluation	$\leftarrow Monitor continually after ICF is signed \rightarrow$										

Note: When scheduled at the same timepoint, the triplicate ECG should be performed first, followed by vital signs assessments, and then PK/PD sampling.

^a All postdose timepoints are relative to the start of the IV infusion/time of the SC injection (ie, time 0 hr) except the ECG, PK/PD sample, and infusion site evaluation performed/collected at the EoI (see footnote d).

^b Only if the Investigator approves the day prior as an Outpatient Visit.

^c Each 12-lead ECG will be performed in triplicate (sequentially within a 15-minute period) and should not be assessed after any major meal (ie, major meals should be withheld until after ECG assessments). At least the last of the 3 predose triplicate 12-lead ECG will be performed within half an hour prior to dosing. The ECGs at 2, 6, and 12 hours postdose have a window of \pm 30 minutes.

^d ECG and PK/PD (in that order) performed/collected at EoI (t_{max}) each have a window of + 15 minutes.

Protocol Amendment 5 10 Mar 2022

ALXN1850-HPP-101

- ^e Vital signs will be measured every 15 minutes for the first hour after dosing, with a window of \pm 5 minutes. Other vital signs measurements have a window of \pm 15 minutes.
- ^f A window of ± 30 minutes from each postdose time point is permitted for all PK/PD timepoints except EoI. Predose PK/PD windows are -1 hour (SC doses) and -3 hours (IV dose).
- ^g Injection/infusion site evaluations will be performed during the infusion, after I/EoI, and then within 15 minutes (+ 5 minutes) after I/EoI. The rest of the timepoints have a window of \pm 15 minutes.
- ^h Predose and postdose abbreviated PEs are allowed at the predose or dosing day, and on the day after dosing or 2 days after dosing, depending on when the participant is admitted and discharged.
- ⁱ If a hypersensitivity reaction is suspected, samples should be collected as soon as possible (within 1 hour of the reaction) and again at 2 and 8 hours (+ 1 hour window each) after the 1st sample. The Day 1 predose sample will only be analyzed for participants with a reported suspected hypersensitivity reaction at any time following the first dose.

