In a monkey 28-day toxicity study, administration of ALXN1850 via SC injection once q3d for 28 days (Days 1, 4, 7, 10, 13, 16, 19, 22, 25, and 28) for a total of 10 doses to male and female cynomolgus monkeys was well tolerated up to 20 mg/kg/dose, the highest dose evaluated in this study. There were no ALXN1850-related changes in injection site reactions (dermal scoring), body weights, body weight gains, qualitative food consumption, ophthalmology, manual respiratory rates, indirect blood pressures, qualitative electrocardiography, hematology, urinalysis, gross pathology, and organ weights. At the end of the dosing phase, there were dose-related increases in ALP activity (anticipated pharmacology effect) which were fully (1 mg/kg/dose) or mostly ($\geq 5 \text{ mg/kg/dose}$) resolved following a 28-day recovery period. Non-adverse ALXN1850 related microscopic changes were confined to the injection sites and included minimal to mild degeneration/necrosis, mineralization, and mixed cell inflammation/infiltration. Partial recovery of degeneration/necrosis and mixed cell inflammation/infiltration of the injection site(s) were observed within the recovery groups, while minimal to mild mineralization persisted in recovery males at $\geq 1 \text{ mg/kg/dose}$ and females at 20 mg/kg/dose. Heart rate increases were observed in all animals at 1 mg/kg/dose and in some of the animals at \geq 5 mg/kg/dose. Heart rate and electrocardiogram (ECG) values remained within a normal range of biological variation for monkeys of this age, and therefore these heart rate increases were not considered to be adverse, given the incongruity with systemic exposure data. In conclusion the dose level of 20 mg/kg/dose is considered to be the NOAEL that corresponds to Day 24 males and females combined mean C_{max} value of 254 µg/mL and mean AUC_{0-72h} value of 15400 h*µg/mL, respectively.

In conclusion, SC administration of ALXN1850 to rats or monkeys did not identify any new or unexpected systemic toxicity or local tolerability findings. The NOAEL dose of 20 mg/kg/dose from the ALXN1850 GLP monkey toxicity study was used to select the Phase 1 study starting dose. The observed exposure of the NOAEL at 20 mg/kg/dose from the GLP SC monkey toxicity

Page 32 of 97	
Alexion Confidential	

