8.2.2. Vital Signs

Vital sign measurements will be taken after the participant has been resting in the supine or semi-recumbent position for at least 5 minutes and will include temperature (°C; tympanic or oral), respiratory rate, blood pressure, and pulse.

The timing of vital sign measurements is described in the SoA (Section 1.3). Of note, vital signs measurements will be performed every 15 minutes for the first hour after dose administration to monitor for anaphylaxis.

Out of range blood pressure or pulse measurements will be repeated at the Investigator's discretion. Confirmed, clinically significant vital sign measurements will be recorded as AEs.

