For the summary statistics of all continuous variables unless otherwise specified, for absolute value, minimum and maximum will be presented to the same number of decimal places as the raw data, mean, median, Q1, Q3, and IQR will be presented to one more decimal places than the raw data, SD will be presented to two more decimal places than the raw data; for percent change, minimum and maximum will be presented to one decimal place, mean, median, Q1, Q3, and IQR will be presented to two decimal places, and SD will be presented to three decimal places. %CV and geometric %CV will be presented to one decimal place, and N and n will be presented to integer.

Percentages will be suppressed when the count is zero and will be presented to one decimal place. The denominator for all percentages will be the number of participants in the cohort for the population of interest, unless otherwise specified.

All tables, listings, and figures will be presented by cohort, unless otherwise specified.

All data listings will be sorted by cohort, participant number, and date-time if applicable.

No algorithm for imputation of missing data will be employed but will be analyzed as missing.

Study days are calculated with respect to the first dose date as below:

- If the assessment/observation date is on or after the first dose date, then Study Day = Assessment/Observation Date First Dose Date + 1;
- Otherwise, Study Day = Assessment/Observation Date First Dose Date

Study weeks are calculated with respect to the first dose for the assessment/observation occurred on or after the first dose as below, unless otherwise specified:

• Study Week = Integer part of (Assessment/Observation Date – First Dose Date)÷7+1

Baseline will be defined as the last non-missing assessment (including repeated and unscheduled assessments) before the first dose of study drug administration, unless otherwise specified.

For summary of safety assessments, if there are repeated measurements at a time point, the first non-missing assessment at that time point will be used in the summary tables.

Unscheduled results will not be included in the summary tables, except for determining Baseline, but will be presented in data listings.

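### SAP Section 9.3 leaves the protocol's first-hour vital-sign readings out of its schedule and its summaries for all four doses

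*SAP*

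**What the plan says.** **Protocol.** Table 3 (Section 1.3) covers every dosing day: Days 1, 15, 22 and 29 for the first participant in a cohort, and Days 1, 8, 15 and 22 for the others. It marks vital signs before the dose, at 15-minute intervals in the first hour, and at 2, 6 and 12 hours. Footnote e gives the first-hour readings their own tolerance: "Vital signs will be measured every 15 minutes for the first hour after dosing, with a window of" 5 minutes either way. The other vital-sign readings have 15 minutes either way. Section 8.2.2 states the purpose: "vital signs measurements will be performed every 15 minutes for the first hour after dose administration to monitor for anaphylaxis".

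**SAP.** Section 9.3 gives the IV dosing day as "Day 1 (pre-dose, 2h, 6h, and 12h post IV" dose and the first participant's first SC dosing day as "Day 15 (pre-dose, 2h, 6h, and 12h post SC" dose 1. The remaining dosing days follow the same pattern. The list of relative times that drives the summary and change-from-baseline tables starts "Baseline, 2 hours post IV dose, 6 hours post IV dose, 12 hours post IV dose, 24 hours" for the IV dose. For each SC dose it goes from pre-dose to 2 hours. Section 9.3 also states: "Vital sign measurement results, including height, weight, and BMI, will be presented in a data listing".

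**SAP, comparison.** Section 9.8 includes the first-hour 15-minute grid for injection and infusion site evaluations, in both its schedule and its summary list.

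**The concern.** The first-hour readings are scheduled assessments with their own window, and the protocol singles out that hour for anaphylaxis monitoring. A programmer who builds the vital-sign tables from SAP Section 9.3 has no row for them at any dose.

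This is a first-in-human study whose primary objective is safety and tolerability, with about five participants per cohort. A table by cohort and time point can show a modest shift in pulse or blood pressure that several participants share and that nobody flags individually. If such a shift came and went within the first hour, the planned summaries would not show it. The SAP gives no reason for leaving the hour out. Because the same Table 3 column was carried into Section 9.8, the omission looks like a drafting slip.

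**Working it through.** The plan states no figure on this point, so the check sets the two schedules side by side and counts.

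**Inputs**
- Doses per participant: 4 (1 IV, 3 SC), Protocol Table 3.
- First-hour readings per dose: 4, reading 15-minute intervals as 15, 30, 45 and 60 minutes. The documents do not list the minutes, so this is an assumption.
- Later dosing-day readings per dose: 3 (2, 6 and 12 hours), in both documents.

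| Post-dose vital signs on a dosing day | Protocol Table 3 | SAP 9.3 |
|---|---|---|
| 15, 30, 45, 60 min | 4 | 0 |
| 2, 6, 12 h | 3 | 3 |
| Total per dose | 7 | 3 |
| Total over 4 doses | 7 × 4 = 28 | 3 × 4 = 12 |

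**Readings without a summary row**
- Per participant: 28 − 12 = 16, and 16/28 = 57% of dosing-day post-dose readings. This is every first-hour reading.
- Against all scheduled post-dose vital signs, the visits on other days are added: 14 for first participants and 13 for subsequent ones (Protocol Tables 1 and 2). The shares are 16/(28 + 14) = 16/42 = 38% and 16/(28 + 13) = 16/41 = 39%.
- Across the study: 16 × 15 = 240 sets of readings if about 15 participants receive all four doses, or 16 × 9 = 144 for the minimum of 9 completers.

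**Could the readings reach a summary of measured values by another route?**
1. Through the 2-hour row: no. The latest 60-minute reading falls at 60 + 5 = 65 minutes, and the 2-hour window opens at 120 − 15 = 105 minutes.
2. Through the ECG heart rate: no. The first post-dose time point in SAP Section 9.5 is also 2 hours.
3. Through the general rules in SAP Section 4: no. These readings are scheduled under the protocol, but a programmer who treats anything off the Section 9.3 list as unscheduled meets this rule: "Unscheduled results will not be included in the summary tables, except for determining Baseline, but will be presented in data listings".

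**The case against.** The strongest reply is that little of clinical importance is lost, and much of it stands.

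- **Adverse events.** Protocol Section 8.2.2 has confirmed, clinically significant vital signs recorded as adverse events, so they enter the TEAE tables. Related changes in heart rate or blood pressure within 24 hours count as injection/infusion-associated reactions, which SAP Section 9.1 tabulates.
- **Listing and later rows.** Every reading is to be listed, and with about five participants per cohort a listing can be read by eye. An effect that lasts to 2 hours has its row.
- **No broken analysis promise.** Protocol Section 9.4.2 commits only to vital-sign summaries by visit. The mismatch is with the Schedule of Activities. Against this, the SAP itself chose several rows within each dosing day, so a by-visit reading does not explain leaving out only the first hour.
- **Escalation.** Under Protocol Section 6.6.1 the Safety Review Committee reviews vital-sign measurements directly and does not depend on these tables.

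A reader might also infer three stronger things, none of which the documents support.

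- *That acute effects never reach any table.* The adverse event route above shows that they can.
- *That the omitted hour is the time of peak IV exposure.* Table 3 places the peak at the end of infusion, but no infusion duration is given. Protocol Section 6.2 leaves the rate to the Pharmacy Manual. The argument would not carry over to the SC doses, which supply 12 of the 16 readings.
- *That the monkey data predict a first-hour effect.* Protocol Section 2.2.2.3 does say "Heart rate increases were observed in all animals at 1 mg/kg/dose and in some of the animals at" higher doses. It adds that the values stayed within normal variation and were not considered adverse, because they did not track exposure. It gives no timing relative to dosing.

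**Conclusion.** The inconsistency is real, and its consequence is limited. What the SAP loses is the tabulated level and change from baseline of pulse, blood pressure, respiratory rate and temperature in the first hour after each dose. The loss matters for transient shifts that no Investigator calls clinically significant. The 57% figure rests on the 15, 30, 45 and 60 minute reading and on a denominator of dosing-day post-dose readings. It measures how much of the schedule has no row, not harm. No participant's monitoring is affected, and no primary endpoint count changes. The point is still worth correcting before the tables are programmed, because the missing hour is the one that the protocol marks out for close observation and no other planned summary of measured values covers it.

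**What to change.** In SAP Section 9.3, add 15, 30, 45 and 60 minutes after the IV dose and after SC doses 1, 2 and 3, both to the schedule table and to the relative-time list. This matches Protocol Table 3 and the grid in SAP Section 9.8. Count the times from time zero as Table 3 defines it (start of the infusion, or time of the SC injection).

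An optional extra is one row per dose for the largest rise and the largest fall from that dose's own pre-dose value in pulse and in systolic and diastolic pressure. The protocol does not ask for this. It uses a different reference from the single baseline before the first dose in SAP Section 4, so it would need its own label.

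The cost is SAP wording and four more rows per dose, taking dosing-day post-dose rows from 12 to 28. No new data, visits or procedures are needed.

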9.4. Physical Examination

A physical examination will include assessments of the general appearance; skin; head, ears, eyes, nose, and throat; neck; lymph nodes; chest; heart; abdominal cavity; limbs; central nervous system; and musculoskeletal system.

Physical examination will be performed at below timepoint:

First participant within each cohort	Subsequent participants within each cohort
Screening	Screening
Day -1/ Day 1	Day -1/ Day 1
Day 2/ Day 3 (48 hours post IV dose)	Day 2/Day 3 (48 hours post IV dose)
	Day 7 (1 week post IV dose),
Day 14 (2 weeks post IV dose)	
Day 17 (48 hours post SC dose 1)	Day 10 (48 hours post SC dose 1),
Day 21 (1 week post SC dose 1)	Day 14 (1 week post SC dose 1)
Day 28 (1 week post SC dose 2)	Day 21 (1 week post SC dose 2),
Day 31 (48 hours post SC dose 3)	Day 24 (48 hours post SC dose 3)

Relative time to dose will be presented for summary statistics which includes: baseline, 48 hours post IV dose, 1 week post IV dose, 2 weeks post IV dose, 48 hours post SC dose 1, 1 week post SC dose 1, 48 hours post SC dose 2, 1 week post SC dose 2, and 48 hours post SC dose 3.

Physical examination results will be classified as Normal, Abnormal Not Clinically Significant, Abnormal Clinically Significant, and Not Examined. The results will be summarized by relative time to dose and by cohort and overall.

Physical examination results will be presented in a data listing.

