1.3. Schedule of Activities

Assessment details can be found in the following SoA tables: Study Overview for the First Participant in Each Cohort (Table 1), Study Overview for Subsequent Participants in Each Cohort (Table 2), and Each Dosing Day for All Participants (Table 3).

Page 17 of 97	
Alexion Confidential	

Assessments	Screening		Treatment Period												EoT/ED	FU/ EoS							
Inpatient (I) or Outpatient (O) ^a	0	I/O	Ι	Ι	I/O	0	0	I/O	Ι	Ι	I/O	0	I/O	Ι	I	I/O	I	Ι	I/O	0	0	0	0
Study Day	-56 to -2	-1	1	2	3	5	8	14	15	16	17	19	21	22	23	28	29	30	31	36	51	65	85
Permitted Day(s) Window						±1	± 1					± 1								± 1	± 3	-3/ +7	-7/ +14
Hours postdose ^b				24	48	96	168			24	48	96			24			24	48	168			
Informed consent ^c	Х																						
Inclusion/ Exclusion Criteria	X	Х																					
Medical history	Х													3									
Demographics	Х		3)						e 3)					Table			3)						
Genetic testing (ALPL gene mutation) ^d	Х		Table 3						SC Dosing Day (See Table					(See Ta			Table						
25-OH vitamin D	Х		ee]						See					y (:			See						
Hepatitis B and C screen	X		ay (See						Day (ng Day			Day (
HIV (Types 1 and 2) screen	Х		IV Dosing Day						osing					Dosing			SC Dosing Day (See						
FSH test ^e	Х		Dos						C D					SC			D D						
Weight	Х	Х	\geq					Х	SC				Х			Х	S						
Height and BMI	Х													1									
Alcohol test	Х																						
Urine drug screen ^f	Х	Х						Х					Х			Х							
Serum pregnancy test ^g	Х													l									
Urine pregnancy test ^g		Х	\geq					Х	s (Х	s		Х	s c	-		Х	Х	Х	Х

Table 1: Schedule of Activities - Study Overview for the First Participant in Each Cohort

Page 18 of 97 Alexion Confidential

	T																						
Assessments	Screening									Т	reati	ment	Perio	od								EoT/ED	FU/ EoS Accoccmant
Inpatient (I) or Outpatient (O) ^a	0	I/O	Ι	I	I/O	0	0	I/O	I	I	I/O	0	I/O	Ι	I	I/O	Ι	Ι	I/O	0	0	0	0
Study Day	-56 to -2	-1	1	2	3	5	8	14	15	16	17	19	21	22	23	28	29	30	31	36	51	65	85
Permitted Day(s) Window						±1	± 1					± 1								± 1	± 3	-3/ +7	-7/ +14
Hours postdose ^b				24	48	96	168			24	48	96			24			24	48	168			
Full PE	Х																						
Abbreviated PE ^h		Х		Х	Х			Х		Х	Х		Х		Х	Х		Х	Х				
Vital sign measurements	X			X	Х	Х	Х			Х	Х	X			X			X	Х	Х	Х	Х	Х
Ophthalmological examination ⁱ	X																					Х	
Renal ultrasound ⁱ	Х													1								Х	
Glycated hemoglobin (HbA1c)	X																						
Hematology labs (except HbA1c)	X	Х		X			Х	Х		Х			Х		X	Х		X		Х		Х	

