Note: Participants who complete the EoT assessments but withdraw/are withdrawn prior to completion of the end-of-study assessments will be considered "completed" and do not require replacement if they completed all prior PK/PD sampling within window and received all doses per the SoA. Participants who withdraw/are withdrawn prior to the end-of-treatment visit should have the end-of-treatment assessments performed, if possible, and will be replaced unless

3 participants in their cohort have already "completed" or are on track to "complete".

^a Visits designated "I/O" may be performed Inpatient or Outpatient at the Investigator's discretion.

^b All postdose timepoints are relative to the start of the IV infusion/time of the SC injection (ie, Time 0) except the vital signs measurements, PK and PD sample, and infusion site evaluation performed/collected at the EoI (see Table 3).

° Signed and dated IEC-approved ICF must be obtained before any study-specific screening procedures are performed.

^d If available, historical results are acceptable, and a confirmatory test is not required.

^e Female participants who claim postmenopausal status will have an FSH test to confirm status.

^f A negative drug screen is required for participant enrollment. Results from drug screens collected at timepoints prior to dosing (Days -1, 14, 21, 28) are not required to confirm a negative result prior to dosing. The drug screen results received after sampling will be noted, and if positive, the participant will be

ALXN1850-HPP-101

Protocol Amendment 5 10 Mar 2022

discontinued from the study. If negative, the results will serve as clearance to proceed with dosing for future pre-dosing days. A positive drug test result for a non-prescribed substance received at any visit will lead to discontinuation

- ^g Pregnancy test must be performed on all participants of child-bearing potential at the specified time points. Additional pregnancy tests may also be performed at any time at the Investigator's discretion.
- ^h Predose and postdose abbreviated PEs are allowed at the predose or dosing day, and on the day after dosing or 2 days after dosing, depending on when the participant is admitted and discharged.
- ⁱ If a potential participant is rescreened, these assessments do not need to be performed again unless more than 12 months will have elapsed between each test and enrollment.

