- ⁿ If the participant is in the clinic, collect the first sample ASAP (preferred) or within 1 hour of the suspected hypersensitivity reaction. The 2 subsequent samples also have a permitted + 1 hour window. If the participant is not in the clinic, these samples do not need to be collected and suspected hypersensitivity reaction will be reported as an AE only. If the suspected hypersensitivity reaction persists beyond 8 hours, the CRU should contact the MM for guidance. Abbreviations: ADA = antidrug antibody; AE = adverse event; ALPL = alkaline phosphatase; ASAP = as soon as possible; BMI = body mass index; C5b-9 = terminal complement complex C5b-9; CRIM = cross-reactive immunological material; CRU = clinical research unit; ECG = electrocardiogram; ED = early discontinuation; EoI = end of infusion; EoS = end-of-study; EoT = end-of-treatment; FSH = follicle stimulating hormone; FU = follow-up; HIV = human immunodeficiency virus; I = inpatient; ICF = informed consent form; IEC = Independent Ethics Committee; IgE = immunoglobulin E; IV = intravenous; MM = medical monitor; NAb = neutralizing antibody; O = outpatient; PA = pyridoxic acid; PCP = phencyclidine; PD = pharmacodynamics; PE = physical examination; P1NP = N-terminal propeptide of type I procollagen; PEA = phosphoethanolamine; PK = pharmacokinetics; PL = pyridoxal; PLP = pyridoxal 5'-phosphate; PPi = inorganic pyrophosphate; PTH = parathyroid hormone; rxn = reaction; CTX-1 (sCTX) = serum Ctelopeptide cross-link of type 1 collagen; SoA = schedule of activities; SC = subcutaneous.

Page 22 of 97 Alexion Confidential	

Protocol Amendment 5 10 Mar 2022

ALXN1850-HPP-101

Assessments	Screening									Trea	atme	ent Pe	eriod								EoT Assessments	FU/ EoS
Inpatient (I) or Outpatient (O) ^a	0	I/O	Ι	I	I/O	0	I/O	Ι	Ι	I/O	0	I/O	Ι	I	I/O	I	I	I/O	0	0	0	0
Study Day	-56 to -2	-1	1	2	3	5	7	8	9	10	12	14	15	16	21	22	23	24	29	43	57	78
Permitted Day(s) Window						±1					±1								± 1	±3	-3/ +7	-7/ +1 4
Hours postdose ^b				24	48	96			24	48	96			24			24	48	168			
Informed consent ^c	Х																					
Inclusion/	Х	Х																				
Exclusion Criteria																						└───┤
Medical history	Х																					\vdash
Demographics	X								 													└──┤
Genetic testing (ALPL gene mutation) ^d	Х		le 3)					ole 3)					e 3)			ole 3)						
25-OH vitamin D	Х		Table					Table					Table			Table						
Hepatitis B and C screen	Х		(See					ee					e T									

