8.3.6. Adverse Events of Special Interest

8.3.6.1. Injection Site Reactions

Injection site reactions (ISRs) are defined as AEs localized to the site of study drug administration that occur at any time during study participation that are assessed by the Investigator as possibly, probably, or definitely related to study drug. AE intensity reporting procedures are outlined in Section 10.3.4.

Injection site reactions may occur at any timepoint after study drug administration. There is no additional laboratory testing required for ISRs.

The Investigator is responsible for monitoring for ISRs in patients throughout the duration of the study. As part of the study-required physical examinations, Investigators should evaluate injection sites for signs of reaction(s).

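### SAP 9.4 tabulates a 48-hour physical examination after SC dose 2 that is not scheduled, and has no row for the 24-hour SC examinations that are

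*SAP*

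**What the plan says.** SAP 9.4 has two parts that matter here. Its collection table lists the examination days, and a sentence below it lists the relative times to be summarised.

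- **Summary list.** For the SC doses it names 48 hours and 1 week after dose 1, then "48 hours post SC dose 2, 1 week post SC dose 2, and 48 hours post SC dose 3". It names no 24-hour time after any SC dose.
- **Collection table.** For SC dose 2 the only entry is "Day 28 (1 week post SC dose 2" for first participants, with Day 21 for the others. For SC doses 1 and 3 the only early entries are at 48 hours. For the IV dose the two days share one entry, "Day 2/ Day 3 (48 hours post IV dose".

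Protocol 1.3, Tables 1 and 2, carries a row "Abbreviated PE" with marks on both the day after dosing and 2 days after dosing for the IV dose and SC doses 1 and 3, and on the day after dosing only for SC dose 2. Footnote h to that row lets the post-dose examination fall "on the day after dosing or 2 days after dosing, depending on when the participant is admitted and discharged".

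Protocol 9.4.2 undertakes to summarise examination results per visit for each administration. SAP 9.4 also places all examination results in a listing.

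**The concern.** A programmer who follows SAP 9.4 literally will build a row for SC dose 2 with no scheduled visit behind it, and will have nowhere to put the examination that was scheduled. For SC dose 2 the summary table would then jump from the dose to the 1-week examination. For SC doses 1 and 3 it would show only participants examined at 48 hours, although footnote h accepts 24 hours instead.

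The protocol's promised by-visit summary would be incomplete for the primary objective, which is safety and tolerability. Protocol 8.3.6.1 also makes physical examinations part of the monitoring for injection-site reactions.

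**Working it through.** The plan gives no figure to reproduce. The check aligns the study-day headers of protocol Tables 1 and 2 with the marks in the abbreviated-examination row, then compares the result with SAP 9.4.

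**Inputs**

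- Dosing days from protocol Table 3: Days 1, 15, 22 and 29 for first participants; Days 1, 8, 15 and 22 for subsequent participants.
- Visit days around SC dose 2: Table 1 runs "21 22 23 28 29 30 31" and Table 2 runs "14 15 16 21 22 23 24".
- Abbreviated-examination marks: Table 1 on Days -1, 2, 3, 14, 16, 17, 21, 23, 28, 30 and 31; Table 2 on Days -1, 2, 3, 7, 9, 10, 14, 16, 21, 23 and 24.

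**Formula.** 24-hour day = dosing day + 1; 48-hour day = dosing day + 2. Days are shown as first / subsequent participants.

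| Dose | Dosing day | 24 h day | Exam marked? | 48 h day | Exam marked? | Early row in SAP 9.4 summary |
|---|---|---|---|---|---|---|
| IV | 1 / 1 | 2 / 2 | yes | 3 / 3 | yes | 48 h (Days 2 and 3 paired in collection table) |
| SC 1 | 15 / 8 | 16 / 9 | yes | 17 / 10 | yes | 48 h only |
| SC 2 | 22 / 15 | 23 / 16 | yes | 24 / 17 | no visit | 48 h only, with no matching collection entry |
| SC 3 | 29 / 22 | 30 / 23 | yes | 31 / 24 | yes | 48 h only |

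For SC dose 2, 22 + 2 = 24 and 15 + 2 = 17. Table 1 goes from Day 23 to Day 28 and Table 2 from Day 16 to Day 21, so neither day is a visit. The day after dosing (22 + 1 = 23; 15 + 1 = 16) is a visit with an examination mark in both tables. It is the only such mark before the 1-week examination on Day 28/21.

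**Comparison within the SAP.** PK (8.2), vital signs (9.3), ECG (9.5), site evaluation (9.8) and PD (10) all have a 24-hour time after SC dose 2 and no 48-hour time. The mismatch is confined to 9.4.

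**Count.** With one Day 23/16 examination per participant dosed, the number without a row runs from 9 (the planned minimum of completers, who receive every dose) to about 15 (planned enrolment, if all receive SC dose 2). After SC doses 1 and 3, the 24-hour examinations without a row number at most 2 × 15 = 30. Those who lose their early entry altogether are only the participants examined solely at 24 hours. The documents do not say how many that will be.

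**The case against.** The strongest reply is that footnote h describes one flexible discharge examination, and that SAP 9.4 already merges the two days for the IV dose under a 48-hour label. By analogy, Day 23/16 could be mapped to the 48-hour row for SC dose 2, which would make this a label error and nothing more. The table shells, which might settle the mapping, are not part of the documents. But the pairing is written for the IV dose only. For SC doses 1 and 3 the collection table names the 48-hour day alone, and for SC dose 2 it names neither early day. The analogy shows how to repair the text; it does not supply the missing rule.

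Three stronger readings are tempting, and the documents do not support them:

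- **The row can hold no data and the examination is never reported.** Footnote h makes an examination 2 days after SC dose 2 conceivable, although no visit is scheduled then and SAP Section 4 keeps unscheduled results out of summary tables. The Day 23/16 result still appears in the listing.
- **About 45 examinations (15 + 30) are lost from the table.** Under footnote h the 24-hour and 48-hour examinations can be alternatives. A participant examined at 48 hours after SC dose 1 or 3 has a row, and may have no 24-hour examination to lose. The figure is only a ceiling.
- **Injection-site reactions would be missed.** Sites are evaluated separately through 24 hours after each SC dose, with a summary row at 24 hours after SC dose 2 (SAP 9.8). Site reactions are summarised as events of special interest (SAP 9.1), and clinically significant abnormal findings are recorded as adverse events (protocol 10.3.1).

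**Conclusion.** The mismatch is real. SAP 9.4 specifies one timepoint with no scheduled visit and omits three that are scheduled. Followed literally, it leaves the only scheduled early examination after SC dose 2 out of the summary table, for 9 to about 15 participants, and drops the early entry of anyone examined only at 24 hours after SC dose 1 or 3. The first count assumes that the scheduled examinations take place and that enrolment lies between the planned minimum of completers and the planned total.

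The consequence is small. This is a descriptive table, data collection is unaffected, no endpoint changes, and every result is listed. It is still worth correcting, because a listing does not deliver the by-visit summary in protocol 9.4.2.

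**What to change.** In SAP 9.4:

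1. Remove the 48-hour row for SC dose 2 from the summary list.
2. Add Days 16/9, 23/16 and 30/23 to the collection table.
3. Use one row per dose labelled 24-48 hours post-dose. For SC dose 2 it holds the 24-hour examination. This extends the IV pairing and fits footnote h. Separate 24-hour and 48-hour rows would split one flexible examination, and with the cohort size as denominator (SAP Section 4) each would look incomplete.
4. State which result counts when a participant is examined on both days, for example the worse classification. Without such a rule, the Section 4 default of taking the first non-missing value at a timepoint could select the 24-hour result and hide a later abnormality.

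The cost is a few lines of SAP text and one table shell. No examination is added or moved, and the protocol does not change.
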